## 15.11 Appendix 11: COVID-19 Contingency Investigator Assessment Phone Visits

Only to be used if a patient is unable to attend the Investigational Site due to COVID-19. Every effort should be made to complete the Study Visit at the Investigational Site.

Please conduct all of the following:

- Phone call to be completed by PI/Sub-Investigator
- Please complete all Patient Reported Assessments as listed in the flowchart below
- Please provide/email copies of Patient Scales to Patients prior to Phone call
- Please document Phone Visit in Source Notes
- Data to be entered into eCRF

Visit	Week 4/ Visit 4	Week 8 / Visit 5	Week 12/ Visit 6	Week 18/ Visit 8 (Follow up 1)	Week 20/ Visit 9 (Follow up 2)
Day	28	56	84	126	140
Visit Window	+/-2 days	+/-2 days	+/-2 days	+/-2 days	+/-2 days
Concomitant Medications	X	X	X	X	X
Adverse Events	X	X	X	X	X
DLQI Questionnaire	X	X	X	X	X
POEM Questionnaire	X	X	X	X	X
PO-SCORAD Questionnaire	X	X	X	X	X
Discuss NRS Pruritus Assessment	X	X	X	X	X
Discuss Athens Insomnia Scale	X	X	X	X	X
Discuss Emollient Use Capture	X	X	X	X	X
Discuss Patient Compliance Log	X	X	X		
Discuss IMP Compliance	X	X	X		
Courier Study Drug	X	X	X

## **Statistical Analysis Plan for Clinical Trial Protocol DS107G-05-AD3**

Study Title	A Randomised, Double-blind, Placebo-controlled Study to Assess the Efficacy and Safety of Orally Administered DS107 in Adult Patients with Moderate to Severe Atopic Dermatitis
Study Medication	DS107 Capsules
Type of Study	Multicenter, double-blind, placebo controlled, 2-arm, Phase II study with 16 weeks of active treatment and a 4 week follow up period
Objectives of Study	
The primary objective is to compare the efficacy of orally administered DS107 versus placebo, in the treatment of adult patients with moderate to severe Atopic Dermatitis (AD).
 
The secondary objective is to assess the safety of orally administered DS107 versus placebo, in adult patients with moderate to severe AD.

Sponsor Study No.	DS107G-05-AD3
EudraCT-No.:	2019-000932-25
AMS Study No.	DS23349
Responsible Biometrician	[name] AMS Advanced Medical Services GmbH
Author	[name] AMS Advanced Medical Services GmbH
Date	Sep 24, 2020
Status of Document	Final Version 1.0
Pages	34

CONFIDENTIAL
--------------

## Change management

Version	Date	Author	Description of changes
0.1	May 19, 2020	[name]	First Draft Version
0.2	Sep 07, 2020	[name]	Second draft Version after Sponsor Review
0.3	Sep 21, 2020	[name]	Third draft Version after second Sponsor Review
1.0	Sep 24, 2020	[name]	Final Version

## List of Abbreviations and Definition of Terms

AD	Atopic Dermatitis
AE	Adverse Event
AIS	Athens Insomnia Scale
AMS	AMS Advanced Medical Services GmbH
ATC	Anatomical Therapeutic Chemical
BDRM	Blind Data Review Meeting
BMI	Body Mass Index
BSA	Body Surface Area
DGLA	Dihomo-Gamma-Linolenic Acid
DLQI	Dermatology Life Quality Index
EASI	Eczema Area and Severity Index
ECG	Electrocardiography
eCRF	electronic Case Report Form
FAS	Full Analysis Set
g	Gram
GLMM	Generalised Linear Mixed Model
ICH	International Conference on Harmonization
IGA	Investigator Global Assessment
IMP	Investigational Medicinal Product
IWRS	Interactive Web Response System
kg	Kilogram
MAR	Missing at Random
MedDRA	Medical dictionary for Drug Regulatory Affairs
MMRM	Mixed Model with Repeated Measures
NRS	Numeric Rating Scale
No.	Number

POEM	Patient Orientated Eczema Measure
PO-SCORAD	Patient Oriented Scoring of Atopic Dermatitis
PPS	Per-Protocol Set
SAE	Serious Adverse Event
SAP	Statistical Analysis Plan
SAS	Statistical Analysis System
SCORAD	Scoring of Atopic Dermatitis
SOC	System Organ Class
SOP	Standard Operating Procedure
TMF	Trial Master File
vIGA-AD TM	Validated Investigator Global Assessment Scale for Atopic Dermatitis
WHO	World Health Organisation

## 1 Introduction

This Statistical Analysis Plan (SAP) refers to the Trial Protocol DS107G-05-AD3, final version 5.0 (EU) and version 5.1 (US) dated March 18, 2020 which includes the previously approved versions of the protocol. The SAP will be finalised before any analysis will be conducted. The specifications included in this SAP which have not been mentioned in the study protocol, are restricted to statistical issues, and have no impact on the clinical conduct of the trial.

This SAP describes the analysis to be performed at the end of the trial.

Additions or changes to the analysis planned in this SAP may be defined during the BDRM (Blind Data Review Meeting) and documented in the BDRM protocol which will be approved by the BDRM participants.

The document is written in compliance with the ICH Guidelines E9 and the *AMS* SOP ST-02.01 (Statistical Analysis Plan).

### 1.1 Study Objectives

The primary objective of this clinical trial is to compare the efficacy of orally administered DS107 (2g) versus placebo, in the treatment of adult patients with moderate to severe AD. The secondary objective is to assess the safety of orally administered DS107 (2g) versus placebo, in adult patients with moderate to severe AD.

It is planned to test the trial medication versus placebo in a total of 220 patients.

### 1.2 General Study Design

This clinical trial will be carried out as a randomised, placebo-controlled, double-blind, parallel group, multi-centre 2-arm Phase 2 study to investigate the efficacy of orally administered DS107 in AD patients.

It is planned that at least 220 patients suffering from moderate to severe AD will be included in this study. All patients will sign an informed consent and undergo screening for study eligibility.

Before the comparative treatment period can commence, patients will return to the site for a baseline assessment of their disease and eligible patients will be randomly allocated to one of the treatment regimens in a 1:1 randomization:

- 2g DS107 (4 DS107 capsules) orally administered once daily for 16 weeks
- Placebo (4 placebo capsules) orally administered once daily for 16 weeks

There is a 4 week follow-up period.

To maintain the double-blind conditions, DS107 capsules and placebo will be identical in appearance.

### 1.3 Study Population

The study population will consist of male and female patients with confirmed diagnosis of AD aged 18 years or older.

## 1.4 Study Medication

The following medication supplies will be used in the study:

### **DS107 capsules:**

Each DS107 capsule contains 500mg DGLA as an active ingredient in an opaque, oval soft gelatin capsule.

### **Placebo capsule:**

Each matching placebo capsule contains 500mg of liquid paraffin in an opaque oval soft gelatin capsule.

## 1.5 Randomisation

Approximately 220 patients will be randomized into double-blind treatment groups in a 1:1 ratio by an IWRS.

- 2g DS107 (4 DS107 capsules) administered once-daily for 16 weeks
- Placebo (4 placebo capsules) orally administered once-daily for 16 weeks

A randomization list permuted by blocks and stratified by site will be generated by the Sponsor or its designee. The randomization schedule with study drug assignments will be generated prior to the start of the study and will be known only to the individuals responsible for labelling the study drug, the statisticians generating the schedule and the IWRS team responsible for implementing the schedule. The IWRS will assign a medication kit number to each patient and the contents will be based on the randomization code.

At the investigational site, each patient will be assigned a patient identifier number during screening that will be used on all patient documentation. The patient identifier number will contain the site number and the patient number assigned in numerical order at the Screening Visit (e.g.: 102-10 for the tenth patient screened at the site number 02). Patient numbers will be assigned in ascending order starting with 01.

The treatment assignment procedure will use blocks of sufficient size to maintain a blind and balance across treatment arms. Following successful completion of the screening/baseline evaluations and confirmation that the patient is eligible for participation, the patient will be randomised to treatment. This will be performed by the Investigator using the IWRS which will assign a medication number to the patient.

## 1.6 Interim Analysis

An interim analysis may be conducted after at least 50% of planned enrolled patients have completed their Week 16 assessments or an early termination visit. The interim analysis will be conducted in accordance with sponsor standard operating procedure (SOP) "Interim Analysis of Clinical Studies".

An unblinded interim analysis will be performed by an unblinded independent statistician. Interim data and the results of interim analyses will not be accessible by anyone other than the unblinded statistician. The sponsor will remain blinded with procedures in place to ensure the confidentiality of the interim data, as per the sponsor SOP "Interim Analysis of Clinical Studies".

The unblinded statistician will make one of the following recommendations to the sponsor based solely upon the primary efficacy endpoints:

- Modify the sample size
- Continue the study as originally planned
- Stop the study due to futility

Further details will be described in an interim statistical analysis plan. No  $\alpha$  adjustment will be executed.

Due to the rapidly evolving COVID-19 situation at both a global and country level, a modification to the prospectively planned sample size may be necessary if patient recruitment is not feasible and must be stopped. The interim analysis will safeguard the integrity of the trial and inform whether further patient recruitment is required when conditions at participating sites are amenable to re-initiation of patient recruitment.

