### **13.12 COVID-19 Contingency**

Due to the unprecedented worldwide COVID-19 pandemic, the Sponsor is implementing measures to assure the safety of trial participants, to maintain compliance with GCP and to minimize risk to trial integrity.

Among these measures are modifications to the protocol to ensure that if difficulties in adhering to protocol-specific procedures or protocol-mandated visits are encountered by patients, investigators or study sites, adequate and appropriate contingencies are in place.

COVID-19 contingency measures do not replace the existing protocol procedures and visit schedule.

The following contingencies and actions will be implemented in response to the evolving COVID-19 pandemic:

1. An interim analysis will be conducted after at least 50% of patients have completed their week 16 or end-of-treatment visits as described in Section 12.9 Interim Analysis. Due to the rapidly evolving COVID-19 situation at both a global and country level, a modification to the prospectively planned sample size may be necessary if patient recruitment is not feasible and must be stopped. The interim analysis will safeguard the integrity of the trial and inform whether further patient recruitment is required when conditions at participating sites are amenable to re-initiation of patient recruitment.
2. In a worst-case scenario where a patient is unable to attend the study site for protocol-mandated visits, due to patient considerations (such as COVID-19 infection or quarantine) or study site restrictions;
  - A. The investigator will complete all possible assessments via phone for all impacted study visits as described in Appendix 11. COVID-19 Contingency Investigator Assessment Phone Visits.
    - Phone visit assessments must include assessment of adverse events, patient-reported efficacy endpoints and compliance.
    - The patient will be reminded that IMP will continue to be administered approximately 2 hours after food consumption at the same time each day. Patients will be reminded to not consume food for approximately 1 hour after IMP administration.
    - The patient will be reminded that NRS for the assessment of pruritus will continue to be captured on a daily basis from screening to the follow-up visit. Emollient use will also continue to be captured on a daily basis for the same period.

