## 2 Sample Size

In the Phase 2a trial, IGA response rates of 21.6% and 11.8% were observed for DS107 and placebo respectively resulting in a difference in response rates of 9.8%. Due to the prolonged treatment period of 16 weeks, a clinically relevant difference in IGA response rates of 15% was expected for the current study.

Assuming a placebo response rate of 12% and a true response rate difference of 15% at Week 16 and using a two-sided Chi-Square test on a significance of 5%, then 220 evaluable patients (110 patients per treatment arm) will be needed for 80% power to detect this difference as statistically significant. As the following table shows, the number of patients needed for the discovery of a 15% response rate difference depends also on the placebo response rate shown in the left column of the table as decimal numbers:

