### 6.1 Primary Endpoint Evaluation

The primary endpoint variables will be:

- the proportion of patients achieving an vIGA-ADTM score of 0 (clear) or 1 (almost clear) and a decrease of at least 2 points in vIGA-ADTM from baseline to Week 16.
- the proportion of patients achieving EASI-75 ( $\geq 75\%$  improvement from baseline) at Week 16.

Both primary endpoints will be analysed using a Generalised Linear Mixed Model (GLMM) with treatment arm, visit, their interaction treatment-by-visit, and baseline vIGA-ADTM value as factors, and with patient as random effect; this model will especially be used to estimate missing data and the treatment effects at Week 16 taking missing data into account. The primary analysis will be based on the FAS, and repeated for the PPS as a supportive sensitivity analysis. Success in either of the primary endpoints denotes successful proof of efficacy.

If rescue medication is used, the patient will be specified as a non-responder from the time the rescue is used.

The handling of missing data in regards with primary statistical analysis and further sensitivity analysis using the jump to reference method to estimate the de facto estimand and analysing patients who received rescue medication as treatment failures are described in section 4.1.5.

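### Control of the 5% level is not shown after an unblinded interim that may change the sample size: SAP 1.6 rules out an alpha adjustment and leaves the size rule to a separate document

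*SAP*

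**What the plan says.** SAP 1.6 allows an unblinded interim once at least 50% of planned patients have Week 16 or early-termination data. On the decision it says: "The unblinded statistician will make one of the following recommendations to the sponsor based solely upon the primary efficacy endpoints". The options are to change the sample size, to continue as planned, or to stop for futility. No direction, floor, cap or conditional-power limit is given for a size change. The section defers the rest: "Further details will be described in an interim statistical analysis plan". It then states that no alpha "adjustment will be executed".

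The same section adds a pandemic reason for a size change: "a modification to the prospectively planned sample size may be necessary if patient recruitment is not feasible and must be stopped". Protocol 13.12 says that the look will also "inform whether further patient recruitment is required when conditions at participating sites are amenable to re-initiation of patient recruitment".

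The final test is not deferred. SAP 1 states: "This SAP describes the analysis to be performed at the end of the trial". SAP 6.1 gives the only such test for the primaries: "Both primary endpoints will be analysed using a Generalised Linear Mixed Model (GLMM) with treatment arm, visit, their interaction treatment-by-visit". It names no stage weights, combination test or adjusted critical value, so I read the test as unweighted, although the SAP does not use that word. The two-sided 5% level appears only in the sample-size sections (protocol 12.3, SAP 2).

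**The concern.** An ordinary test at 1.96 has a 5% level when the final size does not depend on the treatment difference seen so far. Here the size may be chosen by someone who has seen that difference on the primary endpoints. Some size rules leave the level at or below 5%, and others raise it. The plan commits to no adjustment without naming a rule that would justify it.

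At stake is the reading of a primary p-value just under 0.05 after a size change. It may or may not be a 5% finding, and nothing in the plan lets a reader tell. The rule that either primary endpoint suffices is a separate source of inflation and is not counted here.

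**Working it through.** **Inputs.** From SAP 2: 12% v 27%, two-sided 5%, and "then 220 evaluable patients (110 patients per treatment arm) will be needed for 80% power to detect this difference as statistically significant". From SAP 1.6: a look at 50% or later. Assumed here, because the documents give no rule: the look at 110 of 220, caps of 330 and 440, conditional power (CP) at the observed trend, one endpoint, and a normal approximation in place of the GLMM.

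**The plan's own figure.** The pooled-variance chi-square formula gives 108.3 per arm (table: 108.4). At 110 per arm, power is 80.6%, a drift of 2.823. The sample size reproduces.

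**Conditional error.** Let z1 be the interim statistic, t = 0.5, and r = final size / 220. Under the null, the chance that the ordinary final test crosses +1.96 is

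CE(z1; r) = 1 − Φ[(1.96·sqrt(r) − z1·sqrt(t)) / sqrt(r − t)].

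The two-sided level is CE(z1; r) + CE(−z1; r), averaged over z1 ~ N(0,1).

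**Why the rule decides the answer.** Compare 220 (r = 1) with 440 (r = 2):

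- z1 = 0.5 (CP 3.8%): 220 gives 1 − Φ[(1.96 − 0.354)/0.707] = 1.2%; 440 gives 1 − Φ[(2.772 − 0.354)/1.225] = 2.4%. Doubling raises the error.
- z1 = 1.8 (CP 79.6%): 220 gives 1 − Φ[(1.96 − 1.273)/0.707] = 16.6%; 440 gives 1 − Φ[(2.772 − 1.273)/1.225] = 11.0%. Doubling lowers it.
- The two are equal at z1 = 1.20, where CP = 1 − Φ(1.568 − 1.203) = 36%.

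**Level of the ordinary test, look at 110**

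| Assumed size rule | Two-sided level |
|---|---|
| Size fixed at 220 | 5.0% |
| Futility stop below 20% CP, no other change | 4.1%* |
| Increase only at CP 36–80%, cap 440 | 4.7–4.9%* |
| Increase only at CP of at least 50%, cap 440 | 4.95% |
| Increase whenever CP for benefit is below 80%, cap 330 | 5.3% |
| Same, cap 440 | 5.5% |
| Worst-case increase, cap 330 / 440 | 5.8% / 6.2% |
| Recruitment ends at interim p < 0.05, with 22 / 0 patients still in the pipeline | 6.4% / 8.3% |
| Worst case with the size free in 110–220 / 110–440 | 8.7% / 9.9% |

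*Twice the efficacy tail.

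For the 5.3% and 5.5% rules, the efficacy tail is about 2.8% and 3.0% against 2.5%; the other tail stays near 2.5%. If the increase is made only when DS107 is ahead, the totals are unchanged and the efficacy tail is 2.7–2.8%.

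A later look raises the worst-case increase to 5.9% / 6.4% at 60% and 6.1% / 6.7% at 70% (cap 330 / 440).

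**Binary check.** With 400,000 null trials per rule, fixed size / cap 330 / cap 440 gave 5.3% / 5.5% / 5.5% at a 12% response rate and 5.0% / 5.3% / 5.4% at 20%. Part of the excess at 12% is discreteness, since the fixed design itself runs at 5.3%.

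**Stage-weighted test.** Take sqrt(w)·Z1 + sqrt(1−w)·Z2 with w = 110/220 = 0.5. Under the null, Z2 is N(0,1) whatever second-stage size was chosen, so the level is 5.0%. Binary simulation of the two increase rules gave 5.0–5.1%.

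Power is 1 − Φ(1.96 − 2.823·k), where k = sqrt(r) for the ordinary test and k = 0.5 + 0.707·sqrt(r − 0.5) for the weighted test:

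- 220: 80.6% for both.
- 330: 92.6% weighted, 93.3% ordinary.
- 440: 97.1% weighted, 97.9% ordinary.
- 132 (22 second-stage patients): 53% weighted, 59% ordinary.

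At 11 second-stage patients per arm and 12% response, the chance of no responder in at least one arm is 1 − (1 − 0.88^11)² = 43%. A logistic contrast in that stage alone would be unreliable.

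**The case against.** The strongest reply is that the deciding rule sits in an interim SAP we cannot see. If that document confines the interim to a futility stop, or to increases at promising conditional power, then making no adjustment is correct. The SAP's listed options also point to mild rules: it offers a futility stop in the region where an increase does most harm. With observed-trend conditional power, doubling below 80% but not below about 20% stays at or under 5%. The interim is optional under SAP 1.6, the trial is Phase II, and the sponsor stays blinded.

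Much of this stands. It shows that inflation is not established and that the likely excess is modest. It does not show control, because the no-adjustment sentence and the final test are already fixed in this SAP without reference to a qualifying rule. Sponsor blinding limits operational bias but does not remove the effect of choosing the size on the observed difference. SAP 1 and SAP 5 let the blind data review meeting amend methods, but that meeting comes after the interim.

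A reader might infer that the plan allows early success, with a level of 8% to 10%. The text does not support that: no efficacy stop is listed, and the size change is tied to infeasible recruitment. A reader might also reach about 6% by enlarging the trial whenever conditional power is below 80%. That requires the rule to enlarge symmetrically when DS107 looks worse than placebo; a rule aimed at benefit gives 5.3–5.5%.

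**Conclusion.** The point holds as a failure to show control of the 5% level, not as a demonstrated inflation. For increases only, the excess at a look at 110 runs from none to 1.2 points (worst case, cap 440), and about 0.3 to 0.5 points under a plausible benefit-directed rule with no lower limit. Anything from 6.4% upward at that look requires a favourable result to shorten the trial or keep recruitment closed. The documents do not provide for that, but the unrestricted size option and the link to restarting recruitment do not exclude it.

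All these levels rest on assumed rules and caps, one endpoint, and a normal approximation to the GLMM. The matter arises only if the interim is run and the size can change. It should be fixed, because the remedy is cheap and must be in place before unblinding.

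**What to change.** Before unblinding, replace the no-adjustment sentence in SAP 1.6 and adopt one of two routes.

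1. **Weighted test.** Add to SAP 6.1 that, if the interim is run and the size is changed using unblinded data, each primary is tested with sqrt(w)·Z1 + sqrt(1−w)·Z2 at two-sided 5%. Z1 is the Week 16 GLMM contrast in patients in the interim cut. Z2 is the same contrast in all other patients, including the pipeline. w is the number in the cut divided by 220, recorded before unblinding, and the interim decision uses only patients in the cut. Pre-specify a fallback for Z2, such as a Week 16 two-proportion score test, for a second stage too small for the GLMM.
2. **Restricted rule.** Keep the ordinary GLMM test, but limit the interim SAP to increases above a conditional-power limit shown to hold 5% (for example at least 50%), plus the futility stop. Date it before unblinding and cross-reference it in SAP 1.6.

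Under either route, state that the size may not be cut, nor recruitment left closed, because interim results are favourable. A COVID-driven halt decided on blinded operational grounds keeps the ordinary GLMM test, as does a trial with no interim.

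The cost is wording, with no new data. The weighted test loses no power at an unchanged size, under 1 point if the size is raised, and about 6 points if only 22 second-stage patients remain.

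A separate, minor consistency point: SAP 1.6 lists a futility stop that protocol 12.9 lacks, and protocol 12.9 makes the interim optional while 13.12 commits to it. These should be reconciled.

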## 1.7 Time Schedule / Study Duration

Patients will come to the clinic on 8 occasions: at Screening/Visit 1, Baseline/Visit 2, Week 4/Visit 4, Week 8/Visit 5, Week 12/Visit 6, Week 16/Visit 7 (end of treatment), Week 18/ Visit 8 (follow up) and Week 20/Visit 9 (follow-up). A telephone visit will also be performed at Week 1/Visit 3.

Patients who discontinue the study early will be asked to attend the investigative site as soon as possible so that assessments scheduled for Visit 7 can be conducted at an Early Termination visit.

In the event that treatment is occurring, a wash out period of up to 4 weeks may be necessary. At the Screening Visit, after giving informed consent to participate, patients will be assessed using the screening examinations. Eligible patients with confirmed AD using the American Academy of Dermatology Consensus Criteria and who meet all the inclusion criteria and do not meet the exclusion criteria at the baseline visit will be enrolled.

During the treatment period and follow-up period patients will be restricted from using any other treatment for AD, with the exception of the same emollients they have been consistently using since the screening visit.

